3.1.4 End of treatment Visit

Patients that discontinue from treatment will undergo an end of treatment visit, regardless of the reason of discontinuation, approximately 30 days (± 7 days) after the last dose of study medication. In case of allogeneic SCT the end of treatment visit should be performed prior to SCT.

3.1.5 Follow-up Phase

Patients who discontinued for reasons other withdrawal of consent for participation in the trial will be followed every 3 months ± 28 days for event free- and/or overall survival.

A patient may decide to discontinue study treatment. This is not the same as fully withdrawal of consent to participate in the trial and these patients should be encouraged to continue to be followed for event-free and overall survival. If a patient chooses to have no further interaction regarding the study (fully withdrawal of consent), the investigator must provide written documentation of the patient's decision to fully withdraw from the study.

3.2 Study timelines

The planned number of 40 patients was reached. The end of the enrolment period was June 2016. End of study will be defined 2 years after registration of the last patient.

4 SELECTION OF THE STUDY POPULATION

4.1 Target Population

Patients with relapsed/refractory Acute Myeloid Leukemia (AML) according to the inclusion and exclusion criteria below will be enrolled in this study trial. Both male and female patients are enrolled.

The baseline leukemia assessment must have taken place within 2 weeks prior to start of treatment. Under no circumstances are patients, who were once enrolled in this study, permitted to be re-enrolled into the same study.

4.2 Inclusion Criteria

To be eligible for this trial, patients must meet the following criteria:

1. Cytological or histological diagnosis of AML with the exception of promyelocytic leukemia (AML M3)
2. Patients must have relapsed/refractory disease (relapse after stem cell transplantation is permitted) as defined as: patients with <PR after first cycle of induction chemotherapy, or
 - a. patients with <CR(i) after second cycle of induction chemotherapy, or
 - b. patients who relapse after conventional chemotherapy or
 - c. patients who have undergone a single stem cell transplantation and who have relapse of their AML.
3. Men and women aged ≥ 18 years and eligible for standard dose of chemotherapy (7+3);
4. A period of at least 3 weeks needs to have elapsed since last treatment (with the exception of hydroxyurea) before participating in this study. Hydroxyurea induction therapy to reduce peripheral blast counts is permitted prior to initiation of treatment on protocol. Treatment may begin in <3 weeks from last treatment if deemed in the best interest of the patient after discussion with the PI of the study;
5. ECOG performance status ≤ 2
6. Serum biochemical values with the following limits unless considered due to leukemia: creatinine ≤ 2 mg/dl; total bilirubin ≤ 2 x ULN, unless increase is due to hemolysis or congenital disorder; transaminases (SGPT or SGOT) ≤ 2.5 x ULN
7. Ability to swallow and retain oral medication
8. Ability to understand and provide signed informed consent;
9. Cardiac ejection fraction must be $>/=50\%$ (by echocardiography).
10. Willingness and ability to comply with scheduled visits, treatment plans, laboratory tests, and other study procedures.

4.3 Exclusion Criteria

Patients with any of the following will not be eligible for participation:

1. Treatment with any investigational agent within four weeks.
2. Cumulative anthracycline dose (daunorubicin or equivalent) >360 mg/m²
3. HIV infection
4. Presence of any medical or psychiatric condition which may limit full compliance with the study, including but not limited to:
5. Presence of CNS leukemia

6. Unresolved toxicity from previous anti-cancer therapy or incomplete recovery from surgery.
7. For patients after SCT as part of prior treatment:
 - a. Necessity of immunosuppressive drugs
 - b. GvHD > grade 1
8. Any of the following within the 12 months prior to study drug administration: myocardial infarction, severe/unstable angina, coronary/peripheral artery bypass graft, symptomatic congestive heart failure, cerebrovascular accident or transient ischemic attack, pulmonary embolism, deep vein thrombosis, or other thromboembolic event.
9. Ongoing cardiac dysrhythmias of NCI CTCAE Grade ≥ 2 .
10. Other severe acute or chronic medical or psychiatric condition or laboratory abnormality that may increase the risk associated with study participation or study drug administration, or may interfere with the interpretation of study results, and in the judgment of the investigator would make the patient inappropriate for entry into this study.
11. Clinically significant bleeding within 1 month

4.4 Registration of Patients

Patients will be screened for eligibility and eligibility check form/Patient Registration Form will be sent to **GSO mbH**, Hamburg.

Patient eligibility will be reviewed by GSO mbH for all patients participating in the study prior to receiving study treatment.

PROTOCOL SPECIFIC QUESTIONS:

- All eligibility criteria will be checked one by one
- Actual values for the eligibility parameters will be requested when applicable
- Date of written informed consent (day/month/year)

Patient eligibility will be checked by GSO mbH once all screening procedures are completed. There will be no exceptions. Any questions should be addressed to GSO mbH prior to registration.

The eligibility check form/Patient Registration Form will be sent from the site to GSO mbH by email or by fax for evaluation at the following:

GSO mbH
Email: [contact]
[contact]
[contact]

Upon confirmation of eligibility, GSO mbH will assign a patient number and return the signed eligibility check form/Patient Registration Form via fax or email to the site. The Patient Registration Form will confirm the treatment arm in which the patient will participate.

The first planned dose of study drug will be administered within 2 weeks after bone marrow aspirate verification of disease progression.

5 SCHEDULE OF ASSESSMENT AND PROCEDURES

5.1 Study Assessments

5.1.1 Response Assessments

Disease status will be assessed by bone marrow and peripheral blood analysis at the end of each 4-weeks induction and consolidation cycle. Disease status during maintenance will be evaluated by peripheral blood analysis at the end of each cycle and during follow-up after SCT every 3 months \pm 28 days. Bone marrow aspirate during maintenance and FU is required in case peripheral blood analysis is suspicious for progression of disease/relapse. Response is evaluated according to Döhner et al. criteria¹.

5.1.2 Translational, Pharmacodynamic and Pharmacokinetic Analyses (Optional)

5.1.2.1 Baseline Translational Studies

5.1.2.1.1 Leukemic Blast Cell Expansion in Mice

The leukemic blasts isolated from bone marrow aspirates of patients will be expanded in 2-3 NSG mice and then retransplanted into 20 NSG mice for therapeutic experiments. The resulting mouse models of patient leukemias will be used to determine the activity of Selinexor against both the bulk leukemia population and leukemia-initiating cells (LICs) of patient AML cells. Mice transplanted with patient AML cells will be treated with either vehicle control or Selinexor to assess the drug response of the bulk AML population and will then re-transplant at limiting cell dilutions the bone marrow AML cells of the vehicle and Selinexor treated mice into new recipient mice in order to calculate the fold reduction of LICs in response to therapy. The therapeutic response of mouse primagrafts of patient leukemias will be correlated with clinical outcomes of patients enrolled in the trial.

5.1.2.1.2 Leukemic Stem Cell Gene Expression

Recent studies by Eppert et al., 2011 and Metzeler et al., 2013 identified AML stem cell prognostic (42 gene) signature by correlating enrichment for the leukemia stem cell (LSC) expression signature with the clinical outcome.^{25, 26} To analyze the extent of “stemness” of patient AML blasts in response to treatment with Selinexor, we will perform gene expression profiling of leukemic blasts isolated from patients before the start of therapy and 24 hour after the first drug dose. The LSC scores will be calculated based on the extent of the enrichment in the 42 LSC-specific gene signature for patient leukemias and will be used to predict clinical outcome. These experiments will be critical for defining the anti-leukemic activity of Selinexor against LICs of specific patient AML cells and predicting patients’ long-term response to the Selinexor therapy.

5.1.2.2 Pharmacodynamic Studies

5.1.2.2.1 XPO1 Inhibition

Leukocytes will be isolated from patient blood samples collected pre- and post-dosing (\geq 4hr) and total RNA will be isolated to study changes in gene expression before and after exposure to Selinexor. Inhibition of XPO1 (Selinexor target) will be assessed by qRT-PCR of XPO1 and other genes, which are upregulated once XPO1 is inactivated (based on Karyopharm gene chip studies)(e.g., ARRDC3, NGFR, SLC family, PCLO).

5.1.2.2.2 Cytokines

Blood samples will be collected pre- and post-dosing and analyzed for plasma cytokine concentrations. Cytokines include: interleukin 1 alpha (IL1 α), tumor necrosis factor alpha (TNF α), interleukin 6(IL-6), MCP1, interferon gamma (IFN γ), vascular endothelial growth factor alpha (VEGF α), interleukin 8 (IL-8), interferon alpha (IFN α), interleukin 10 (IL-10).

5.1.2.3 Pharmacokinetics of Selinexor

Blood samples will be obtained pre- and post-first Selinexor dose of induction cycle 1 to determine Selinexor plasma concentrations.

5.1.3 Safety Assessments

Throughout the treatment period until one month after the last dose of study medication, patients will be assessed for all adverse events. Common terminology criteria for adverse events (CTCAE v4.03, see Appendix 7) will be used for grading. If necessary, the patient may be withdrawn from the study treatment.

Medical history including leukaemia and treatment history will be reviewed and recorded at the screening visit.

Concomitant medications will be documented throughout treatment phase until the EOT visit.

Adverse events (see also Section 7.1): All patients will be closely monitored for adverse events from start of treatment, i.e. cycle 1 day 1, until 30 days after the last dose of study medication. Adverse events for which the relationship to test drug is not “unrelated” should be followed up until they have returned to baseline status or stabilised. Adverse events will be recorded at each visit.

5.1.4 Laboratory Assessments

Safety blood samples include complete blood count, time of recovery of platelets $\geq 50 \times 10^9/L$ and $\geq 100 \times 10^9/L$, ANC recovery $\geq 0.5 \times 10^9/L$ and $\geq 1.0 \times 10^9/L$, clinical chemistry, including liver function test and coagulation.

5.2 Study Procedures

The Schedule of Study Events is displayed in tabular form as Table 2.

Table 2: Schedule of Assessments during the study

Assessments by Visit	Screening	Baseline	Induction cycle(s)		Consolidation (if applicable)	Maintenance (if applicable)	End of treatment	Follow-up ¹⁹
Time window	Within 14 days prior to registration	After registration, before Day1 of induction	During Treatment Twice weekly	End of Cycles	weekly (D2,8,15,21 ± 2 days)	Twice per cycle D1,15 ± 2 days)	30-days after last dose/prior to SCT	Every 3 months ± 28 days
Informed consent ¹	X							
Inclusion and exclusion criteria	X							
Demographics	X							
Medical history ²	X							
Pregnancy test (if applicable) ³	X							
Physical examination and ECOG ⁴	X		X	X	X	X	X	
Body height and weight ⁵	X			X	X	X	X	
BSA	X							
Vital signs ⁶	X		X	X	X	X	X	
Standard clinical neurologic examination	X							
12-lead ECG	X			X	X	X		
Cardiac ultrasound ⁷	X			X			X	
Hematology ⁸	X		X	X	X	X	X	X
Hematological Recovery status ²¹			X ²¹	X ²¹	X ²¹	X ²¹	X ²¹	X ²¹

Assessments by Visit	Screening	Baseline	Induction cycle(s)		Consolidation (if applicable)	Maintenance (if applicable)	End of treatment	Follow-up ¹⁹
Calculation ⁹ (or measurement) of GFR	X			X	X		X	
Clinical Chemistry ¹⁰	X			X	X	X	X	
Urine analysis ¹¹	X			X	X ¹¹	X ¹¹		
Coagulation test ¹²	X		X	X	X ¹²	X ¹²		
HIV testing ¹³	X							
Assessment of signs and symptoms, AE	X		X	X	X		X	
CTCAE v 4.03 scale toxicity			X	X	X	X	X	
Concomitant medication	X		X	X	X	X	X	
Bone Marrow Aspirate ¹⁴	X			X	X	X ¹⁴		X ¹⁴
Survival								X
Selinexor baseline dose ¹⁵		X						
Bone Marrow aspirates for translational research ¹⁶ (optional)		X						
Blood draws for translational research ¹⁷ (optional)			X		X			
Blood draws for Pharmacokinetics ¹⁸ (optional)			X					
Ophthalmological examination ²⁰	X							

Notes

¹ Prior to the first study-specific measures

² Medical history includes baseline symptoms as well as a detailed history of prior cancer therapies including start and stop dates, response of prior cancer therapies, disease progression during or after therapy, as well as discontinuations due to intolerance or any other serious illness.

³ Applicable for women of childbearing potential. Serum β-HCG test within 7 days before the first dose of study drug. To be repeated by urine test, if date of first result exceeds the 7-day window

⁴ Full physical examination for baseline and end of study visit. Physical examinations during the study should be symptom directed.

⁵ Body height will be measured at screening only.

⁶ Vital signs: blood pressure, pulse and temperature

⁷ Echocardiography of left ventricular ejection fraction (LVEF) to observe cardiac toxic city of idarubicin. at baseline, before a second facultative induction course and before first consolidation therapy. Maybe repeated if clinically indicated.

⁸ Hematology: hemoglobin,red blood cell (RBC) count, platelets, white blood cell (WBC) count and WBC differential (neutrophils, lymphocytes), leukemic blasts.

⁹ Calculated GFR according to the formula of Cockcroft and Gault.

¹⁰ Clinical chemistry: Sodium, Potassium, Calcium, Creatinine, Total Bilirubin, Alkaline Phosphatase, alanine aminotransferase (ALT), aspartate aminotransferase (AST), Total Protein, Albumin, LDH

¹¹ Urine analysis will include urine bilirubin, glucose, hemoglobin, ketones, pH, protein (once per cycle in consolidation/maintenance)

¹² Coagulation test include prothrombin time (PT) and activated partial thromboplastin time (aPTT) (once per cycle in consolidation/maintenance)

¹³ If not performed within the last 6 months

¹⁴ Including cytogenetic, flow cytometry and molecular analysis (FLT3 ITD or TKD mutation or NPM-1 mutation, FLT3 ITD at baseline only) at baseline, end of each induction and consolidation cycle. In maintenance and FU after SCT if blood count is suspicious for progression of disease/relapse.

¹⁵ Baseline Selinexor dosing: single dose given after registration but before beginning of first induction cycle.

¹⁶ Bone marrow aspirates for translational research will be taken prior to baseline Selinexor dose and 24 hour post-baseline dose. 2 ml of each aspirate will be used to isolate viable cells for mouse studies; 2 ml of each aspirate will be processed to isolate RNA for stem cell expression array analysis.

¹⁷ Blood draws for translational research (exploratory pharmacodynamic analysis): (2 x 2.5 ml for XPO1 inhibition in leukocytes, 2 ml for cytokines) will be collected on day of first in-clinic dose of Selinexor during each induction and consolidation cycle. 2 x 2.5 ml, plus 2 ml blood will be collected pre-dose and 2 x 2.5 ml will be collected 4 hr post-dose.

¹⁸Blood draws (2 ml) for PK analysis will be performed during first induction cycle on day of first in-clinic dose of Selinexor: pre-dose, 2 hr and 4 hr post-dose.

¹⁹ Follow-up is to include all patients, including those having undergone SCT

²⁰ required at screening and if clinically indicated during the treatment phase. Ophthalmologic examination includes:

- prior to dilation: best corrected visual acuity and slit lamp examination including tonometry
- following dilation: fundoscopy and a slit lamp exam to document lens clarity. If a cataract is seen during the exam, cataract will be graded according to the Lens Opacities Classification System III (LOCS III)

²¹ Hematological Recovery status: platelet recovery $\geq 50 \times 10^9/L$ and $\geq 100 \times 10^9/L$, ANC recovery $\geq 0.5 \times 10^9/L$ and $\geq 1.0 \times 10^9/L$ reached and date of recovery. Until recovery of platelets and ANC, hematology assessments are done as often as necessary to determine the exact date of recovery of platelets and ANC

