------------------	---

	
on Monday and Wednesday or on Tuesday and Thursday or on Wednesday and Friday).
 
Treatment will continue until progression of disease (PD) or unacceptable toxicity, withdrawal of consent by the patients, or non-compliance by the patient with protocol requirements.
 
Patients for whom none of the above mentioned is achieved after 2 4-week induction cycles will have their end of treatment and will be followed for overall survival.

Primary Endpoint	Percentage of patients achieving a complete response (CR) or CRI (complete remission without normalization of peripheral blood counts)
Secondary Endpoints	
 • Partial response rate • Percentage of patients undergoing subsequent allogeneic stem cell transplant • Early death rate • Overall survival (OS) • Event-free survival (Events are defined as Death, not achieving a CR or CRI, Relapse after CR or CRI) • Toxicity (acc. to NCI CTC AE v4.03)
Exploratory Endpoints (Optional Studies)	
 • Limited pharmacokinetics to measure plasma concentration of Selinexor • Selinexor-induced changes in mRNA levels of XPO1 and tumor suppressor markers • Selinexor-induced changes in plasma cytokine levels • Selinexor-induced changes in gene expression profiling of leukemic blasts isolated from patients • Expansion of leukemic blasts in mice for therapeutic studies
Efficacy assessment	
Clinical and Bone Marrow Aspirate examinations and safety assessments are performed at baseline, at the End of induction cycles and if applicable at the end of each consolidation cycle. Disease status during maintenance will be evaluated at the end of each cycle and Follow-up after SCT every 3 months ± 28 days
 
If a patient discontinues treatment due to any other reason than disease progression/ death/ withdrawal of informed consent, the disease evaluations shall continue until definition of relapse-free survival are met. This includes patients who wish to discontinue treatment, but agree that further data is captured for the purpose of the study (partial withdrawal).

Safety assessment	All adverse events occurring during the course of the trial and for up to 30 days after the last dose of study medication will be captured, documented and reported. Toxicity will be graded twice weekly during treatment.

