5.2.4 Treatment Phase

During the treatment phase the following assessments are to be performed according to the study flow chart within the allowed visit windows:

Physical examination and vital signs	
 • Body weight • BSA • Blood pressure, pulse, temperature • Physical examination (symptom directed)
ECOG performance status	Please refer to Appendix 4
Cardiac evaluation	12-lead ECG, cardiac ultrasound
Urine analysis	Urine bilirubin, glucose, hemoglobin, ketones, pH, protein
Hematology	Hemoglobin, white blood cell (WBC) count, neutrophils, lymphocytes, platelets, leukemic blasts
Clinical chemistry	Sodium, Potassium, Calcium, Creatinine, Total Bilirubin, Alkaline Phosphatase, alanine aminotransferase (ALT), aspartate aminotransferase (AST), Total Protein, Albumin, LDH
Coagulation tests	prothrombin time (PT) and activated partial thromboplastin time (aPTT)
Assessment of disease status	Bone Marrow Aspirate, peripheral blood analysis as above
Assessment of hematological recovery status	Platelet recovery $\geq 50 \times 10^9/L$ and $\geq 100 \times 10^9/L$, ANC recovery $\geq 0.5 \times 10^9/L$ and $\geq 1.0 \times 10^9/L$ reached and date of recovery
Adverse events and concomitant medication	Assessed on an ongoing basis.
Blood draws for translational research (optional)	2 x 2.5 ml for XPO1 inhibition in leukocyte assays and 1 ml for cytokine assays will be collected on day of first in-clinic dose of Selinexor during each induction and consolidation cycle. 2 x 2.5 ml, plus 1 ml blood will be collected pre-dose and 2 x 2.5 ml will be collected 4 hr post-dose
Blood draws for pharmacokinetics (PK, optional)	Blood draws (2 ml) for PK analysis will be performed during first induction cycle on day of first in-clinic dose of Selinexor: pre-dose, 2 hr and 4 hr post-dose.

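### The sampling instructions list a cytokine aliquot before dosing only, contradicting the section that calls for cytokine blood before and after dosing

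*Protocol*

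**What the plan says.** The endpoint "Selinexor-induced changes in plasma cytokine levels" appears in the protocol synopsis under Exploratory Endpoints (Optional Studies) and again among the exploratory objectives in section 2.3.

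The methods section, 5.1.2.2.2, says: "Blood samples will be collected pre- and post-dosing and analyzed for plasma cytokine concentrations". It gives no clock time and no volume.

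The volumes and times are given in three other places:

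- **Protocol section 5.2, Table 2, note 17.** Allocation by assay: "2 x 2.5 ml for XPO1 inhibition in leukocytes, 2 ml for cytokines". Allocation by time: "2 x 2.5 ml, plus 2 ml blood will be collected pre-dose and 2 x 2.5 ml will be collected 4 hr post-dose".
- **Protocol section 5.2.4.** Allocation by assay: "2 x 2.5 ml for XPO1 inhibition in leukocyte assays and 1 ml for cytokine assays will be collected". Allocation by time: "2 x 2.5 ml, plus 1 ml blood will be collected pre-dose and 2 x 2.5 ml will be collected 4 hr post-dose".
- **SAP Appendix 19.1, note 17.** The same volumes and times as the protocol's note 17.

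Note 17 and section 5.2.4 repeat these draws in every induction and consolidation cycle. Section 5.1.2.2.1 uses blood from both time points for leukocyte RNA (XPO1). Note 18 adds 2 ml PK draws before dosing and at 2 and 4 hours, in the first induction cycle only.

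**The concern.** A change induced by a dose needs a value before the dose and a value after it. Section 5.1.2.2.2 promises both. The instructions that a site would work from designate cytokine blood only before the dose, and they disagree on how much of it to take.

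A reader of section 5.1.2.2.2 would expect paired cytokine data. A site following note 17 or section 5.2.4 to the letter would not supply them. The endpoint would then lack its post-dose half, or would be replaced in the report by some other contrast that nobody had specified.

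**Working it through.** No sample size, power or error rate bears on this point, and the plan states no figure to reproduce. The check is a reconciliation of volumes.

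**Step 1. Volume left for cytokines.** For each instruction and time point: volume left = volume drawn − volume allotted to XPO1. The XPO1 allotment is 2 x 2.5 = 5 ml in all three places.

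| Source | Time | Drawn | XPO1 | Left for cytokines |
|---|---|---|---|---|
| Protocol Table 2 note 17; SAP 19.1 note 17 | pre-dose | 5 + 2 = 7 ml | 5 ml | 2 ml |
| Protocol Table 2 note 17; SAP 19.1 note 17 | 4 hr post-dose | 5 ml | 5 ml | 0 ml |
| Protocol 5.2.4 | pre-dose | 5 + 1 = 6 ml | 5 ml | 1 ml |
| Protocol 5.2.4 | 4 hr post-dose | 5 ml | 5 ml | 0 ml |

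The pre-dose remainder equals the stated cytokine aliquot in each case, so the allocation is being read as intended. The post-dose remainder is zero in each case. The two volumes, 2 ml and 1 ml, cannot both be the instruction.

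**Step 2. Other post-dose blood on the day.** The post-dose XPO1 blood is for leukocyte isolation and RNA (section 5.1.2.2.1). The PK blood at 2 and 4 hours is assigned to PK and exists only in the first induction cycle (note 18). Neither is assigned to cytokines anywhere, so neither is counted.

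**Step 3. Cost of adding the aliquot at 4 hours.**

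- 2 ml aliquot: the 4-hour draw goes from 5 to 7 ml, and the day's total from 7 + 5 = 12 ml to 14 ml.
- 1 ml aliquot: the 4-hour draw goes from 5 to 6 ml, and the day's total from 6 + 5 = 11 ml to 12 ml.

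**Step 4. Are any draws still to come?** Enrolment ended in June 2016 (section 3.2), and this protocol version is dated 13 January 2017. Draws occur in at most 2 induction plus 3 consolidation cycles of 4 weeks (section 3.1.2). Assume registration on 30 June 2016 and a start two weeks later (the limit in section 3.1), on 14 July. The fifth cycle then starts 4 x 4 = 16 weeks after that, on about 3 November 2016. That is roughly ten weeks before this version was issued. Unless cycles were delayed substantially, few or no cytokine draws remained.

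**The case against.** The strongest reply is that section 5.1.2.2.2 is part of the plan and does ask for cytokine blood after dosing. That stands. A reader might infer from note 17 that the plan takes no post-dose cytokine blood and that the endpoint cannot be computed for any patient. The documents do not support this. They contradict each other, and they do not show which instruction the sites followed. If sites followed section 5.1.2.2.2, paired values exist.

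It can also be said that pre-dose samples recur in each cycle, so some change can be calculated. That is true but weak. It needs at least two sampled cycles, and it reflects the chemotherapy given in between and the course of the disease as well as Selinexor.

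The third reply is that little hangs on this. That also stands. The sub-study is optional and exploratory, and the SAP lists no cytokine variable, analysis or table.

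A reader might further infer that the optional Selinexor dose before induction spoils the cycle 1 pre-dose values, since those patients have already been exposed. The exposure is real, but the documents reviewed do not show that it matters:

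- The interval to the first induction dose is not fixed, and no size of carry-over is given.
- The endpoint is a within-patient change, and section 5.1.2.3 ties the PK baseline to the first dose of induction cycle 1, with no promise of a drug-naive value.
- Section 6.2.3 already requires every dose to be recorded in the CRF with its date and time, so these patients can be identified.

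This is not carried forward as a defect.

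**Conclusion.** The point holds as a contradiction within the documents. Table 2 note 17, section 5.2.4 and the SAP schedule all allot 0 ml to cytokines after the dose, against section 5.1.2.2.2. They also differ on the aliquot, 2 ml against 1 ml. Because the three agree on the missing post-dose aliquot, a single slip in one footnote does not explain it.

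The consequence is conditional. If the listed volumes were followed, the exploratory endpoint has no post-dose value in any cycle. This assumes that no blood assigned to another assay was used for cytokines, which the documents neither provide for nor rule out.

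Severity is low, because the effect is confined to one optional exploratory endpoint.

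**What to change.** 1. Reconcile section 5.1.2.2.2, Table 2 note 17, section 5.2.4 and the SAP schedule note 17. State one cytokine volume, and add that aliquot to the existing 4-hour draw for any cycle still to be sampled.
2. For cycles already sampled, state in the study report what was collected: which time points, what volume, and in how many patients and cycles.
3. If no post-dose aliquot exists, do not report a Selinexor-induced cytokine change. Describe pre-dose levels by cycle only, and note that differences between cycles are confounded by chemotherapy.

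The cost is the 1 to 2 ml per sampling day worked out above, with no extra visit or needle stick, plus one corrected instruction and a sentence or two in the report. Because enrolment has closed, the second and third items are probably the ones that matter.
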